2.3 TERTIARY ENDPOINTS

1. Change in MSFC score from baseline to Week 96
2. Time to Confirmed Disability Progression (CDP) for at least 24 weeks
3. Time to Confirmed Disability Improvement (CDI) for at least 12 weeks
4. Time to Confirmed Disability Improvement (CDI) for at least 24 weeks
5. Health outcomes (MSQoL-54 (inclusive of SF36); FIS, hospitalization, steroid use, time out of work)
6. Total volume of Gd enhancing T1 lesions per MRI scan over the treatment period
7. Volume of T2 lesions
8. Volume of hypointense T1 lesion component (black holes)
9. Proportion of subjects free of disability progression at 24 weeks, 48 weeks, and 96 weeks
10. Proportion of subjects with a relapse
11. Time to first confirmed relapse

3 STUDY POPULATION

3.1 INCLUSION CRITERIA

Subjects must meet the following inclusion criteria to be eligible for participation in this study:

1. 18-55 age
2. Diagnosis of RMS (McDonald criteria 2010; Appendix C)
3. ≥ 2 relapses in prior 2 years or 1 relapse in the year prior to screening and/or ≥ 1 Gd enhancing lesion
4. Documented MRI of brain with abnormalities consistent with MS
5. Active disease
6. EDSS 0-5.5 (inclusive) at screening
7. B cell counts $\geq 5\%$ of total lymphocytes
8. Neurologic stability ≥ 30 days prior to screening and baseline
9. Female subjects who are not of child-bearing potential, have documented surgical sterilization (see Appendix A), and female subjects of child-bearing potential who have a negative serum pregnancy test at baseline. Female subjects of child-bearing potential (see Appendix A), and all male partners must consent to use a medically/clinically acceptable method of contraception throughout the treatment period and for 20 weeks after the cessation of active treatment. Female subjects of child-bearing potential (see Appendix A) must agree to undertake urine pregnancy tests every 4 weeks during active treatment and the follow up period.
10. Fertile male subjects participating in the study who are sexually active with women of child bearing potential, must agree to use a condom during the treatment period and for an additional 20 weeks after cessation of active treatment. Agree to use an accelerated elimination procedure after the last dose of study medications or early termination from the study (see Section 6.10.1)
11. Willingness and ability to comply with trial and follow-up procedures, give written consent

3.2 EXCLUSION CRITERIA

Subjects who meet any of the following exclusion criteria are not to be enrolled to this study:

1. Treatment with Anti-CD20 or other B cell directed treatment
2. Treatment with the following therapies at any time prior to randomization:
 - Alemtuzumab
 - Natalizumab,
 - Teriflunomide,
 - Leflunomide, and
 - Stem cell transplantation
3. Contraindications to teriflunomide or incompatibility with use of teriflunomide.
4. Therapies that are disallowed (minimum of 4 weeks prior to randomization): phenytoin, warfarin, tolbutamide, St John's Wort or cholestyramine
5. Prior DMT exposure within months of screening:
 - a. 24 months with cladribine
 - b. 6 months with daclizumab, azathioprine, methotrexate, or cyclophosphamide
 - c. 90 days with fingolimod, or experimental S1P modulators, IV immunoglobulin, and plasmapheresis
 - d. 30 days with glatiramer acetate, interferons, dimethyl fumarate, laquinimod or glucocorticoids
6. Diagnosed with Primary Progressive MS (PPMS)
7. Pregnant or nursing
8. ≥ 10 years disease duration from onset with subjects EDSS ≤ 2.0
9. Contraindication for MRI and/or gadolinium

10. Known presence of other neurologic disorders that may mimic MS
11. Current evidence or known history of clinically significant infection including:
 - a. Chronic or ongoing active viral, bacterial, or fungal infectious disease requiring long term systemic treatment such as, but not limited to: PML, chronic renal infection, chronic chest infection with bronchiectasis, tuberculosis (TB), or active hepatitis C
 - b. Previous serious opportunistic or atypical infections
 - c. History of positive serology for hepatitis B or hepatitis C or HIV
12. History of clinically significant CNS trauma (e.g., traumatic brain injury, cerebral contusion, spinal cord compression)
13. History of liver disease, including but not limited to:
 - a. Known history of active hepatitis B or C any time prior to randomization or known history of active hepatitis A within 3 years prior to randomization
 - b. Presence of clinically significant chronic liver or biliary disease
 - c. Moderate or severe hepatic impairment defined as Child Pugh Score B or C, respectively, based on measurement of total bilirubin, serum albumin, International Normalized Ratio (INR) and as well as on presence /absence and severity of ascites and hepatic encephalopathy
 - d. Any of the following abnormal laboratory values at screening or first infusion:
 - ALT/SGPT>2X the Upper Limit of Normal (ULN)
 - AST/SGOT>2X ULN
14. Previous diagnosis with a congenital or acquired immunodeficiency (AIDS)
15. History of renal impairment, including, but not limited to:
 - a. Hypoproteinemia (e.g., in case of severe renal disease or nephrotic syndrome) with serum albumin <3.0 g/dL
 - b. Severe renal insufficiency requiring renal dialysis
16. Past or current history of medically significant adverse effects (including allergic reactions) from:
 - a. Corticosteroids
 - b. Diphenhydramine
 - c. Murine or mouse/human chimeric antibodies
17. Subjects with significantly impaired bone marrow function or significant anemia, leukopenia, or thrombocytopenia
 - a. Hematocrit <24% and/or
 - b. Absolute white blood cell count <4,000 cells/mm³ and/or
 - c. Platelet count <150,000 cells/mm³ and/or
 - d. Absolute neutrophil ≤ 1,500 cells/mm³
18. Absolute lymphocyte counts less than 1000/microliter
19. Any severe and/or uncontrolled medical conditions or other conditions that could affect their participation in the study such as:
 - a. Symptomatic, or history of documented congestive heart failure (New York Heart Association functional classification III-IV [see Appendix B])
 - b. QTcF: Female >450 msec; male > 430 msec Angina not well-controlled by medication
 - c. Poorly controlled or clinically significant atherosclerotic vascular disease including cerebrovascular accident (CVA), transient ischemic attack (TIA), angioplasty, cardiac or vascular stenting in the past 6 months prior to screening
20. Other significant concurrent, uncontrolled medical condition including, but not limited to, cardiac, renal, hepatic, hematological, gastrointestinal, endocrine, immunodeficiency syndrome, pulmonary, cerebral,

psychiatric, or neurological disease which could affect the subject's safety, impair the subject's reliable participation in the trial, impair the evaluation of endpoints, or necessitate the use of medication not allowed by the protocol, as determined by the PI of the trial

21. Current participation in any other interventional clinical trial. Participation in non-interventional trial requires approval by the Sponsor
22. Inability or unwillingness to comply with study and/or follow-up procedures outlined in the protocol
23. Lack of immunity to varicella as determined by screening based on the level of VZV IgG. Subject may receive vaccine and be rescreened
24. Vaccination with live virus within 2 months of randomization
25. History or presence of malignancy (except for surgically excised basal or squamous cell skin lesions), lymphoproliferative disease, or history of total lymphoid irradiation or bone marrow transplantation

3.3 DISCONTINUATION FROM STUDY TREATMENT

Subjects will be discontinued from trial treatment or withdrawn from the study for any of the following reasons:

- Irreversible or intolerable toxicity or abnormal laboratory values thought to be related to drug toxicity
- Subject requests to withdraw consent or discontinue treatment
- Pregnancy (see Section 3.3.1)
- Inability of the subject to comply with trial requirements
- Conditions requiring therapeutic intervention not permitted by the protocol
- Inter-current illness (this will be at the Principal Investigator and/or Treating Neurologist discretion)
- Malignancy
- Discontinuation of the study by the Sponsor

After discontinuation from protocol treatment all subjects (other than those who withdraw consent and refuse to enter into the 20 week Follow-up Period) should undergo an accelerated teriflunomide elimination procedure with either oral cholestyramine or oral activated charcoal and be followed for safety for 20 weeks after their last dose of ublituximab/oral placebo or teriflunomide/IV placebo. All new AEs occurring during this period must be reported and followed until resolution, unless, in the opinion of the PI and/or Treating Neurologist, these values are not likely to improve because of the underlying disease. In this case the PI and/or Treating Neurologist must record his or her reasoning for this decision in the subjects' medical records and as a comment on the electronic Case Report Form (eCRF).

All subjects who have Common Terminology Criteria for Adverse Events (CTCAE; Ver 4.03) grade 3 or 4 laboratory abnormalities at the time of discontinuation from protocol treatment must be followed until the laboratory values have returned to grade 1 or 2, unless it is, in the opinion of the PI and/or Treating Neurologist, not likely that these values are to improve because of the underlying disease. In this case, the PI or Treating Neurologist must record his or her reasoning for making this decision in the subjects' medical records and as a comment on the eCRF.

Any subject that withdraws their consent to participate in the study will have all data collection stop on that day and will not be followed-up on. These subjects, however, could be followed further if they agree to sign the Early Termination ICF and enter the 20 week Follow-up Period.

3.3.1 PREGNANCY

During the course of the trial, all female subjects of childbearing potential (the definitions of "women of childbearing potential" are listed in Appendix A) must contact the PI and/or Treating Neurologist immediately if they suspect that they may be pregnant (a missed or late menstrual period should also be reported to the PI and/or Treating Neurologist).

If an investigator suspects that a subject may be pregnant during the study, the trial drugs must be withheld immediately, until the result of the pregnancy test is confirmed. Subjects will proceed with a urine pregnancy test immediately. If the urine pregnancy test is positive, the subject should be informed of the potential teratogenic effects, therefore consideration to withhold further teriflunomide/oral placebo dosing should be made and follow-up appointment should be scheduled as soon as possible where a serum pregnancy test will be performed for confirmation.

If a pregnancy is confirmed via serum pregnancy test, the trial drugs must be stopped immediately and permanently. The subject will complete the Withdrawal from Treatment Visit as soon as possible and will then enter the 20-week Follow-up Period inclusive of accelerated teriflunomide elimination procedure with either oral cholestyramine or oral activated charcoal. The subject will be expected to complete the full Follow-up Period regardless of the outcome of the pregnancy. The investigator must record the pregnancy on a Pregnancy Report Form within 24 hours of learning of its occurrence (see Section 9.10.6 for more details on pregnancy reporting).

Additionally, if a pregnancy is confirmed, the subject will be asked to sign an informed consent form to allow the collection of medical information of both the subject and her baby throughout the pregnancy and until 6 months after the baby is born, as permitted by local regulations. Where required by local regulations, the consent of the father will also be obtained.

If a male subject's female partner becomes pregnant and the male subject has taken at least one dose of study medications (ublituximab/oral placebo or teriflunomide/IV placebo), the pregnancy and newborn will also be followed. In this case, the subject's partner will be asked to sign an informed consent form to allow the collection of medical information of both the mother and baby throughout the pregnancy and until 6 months after the baby is born, as permitted by local regulations. Where required by local regulations, the consent of the male subject will also be obtained. If the mother is younger than legal age, her parent(s)/guardian(s) will also need to give consent, as required by local regulations.

Prior to discharge from the study, all subjects will be counseled by the treating team to have their teriflunomide plasma concentration re-measured prior to attempting to become pregnant or trying to impregnate their female partner.

Confirmed pregnancy must be reported to pharmacovigilance.

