Management of thrombocytopenia and anemia are per institution guidelines and if in the opinion of PI and/or Treating Neurologist, are appropriate for subject care.	

Worst CTCAE Grade Toxicity	Action to be Taken
Elevated Liver Enzymes (ALT and AST)	
Grade	Management
≤ Grade 1	No action required.
Grade 2, 3 or 4 1st and subsequent occurrences	
Withhold study medications (both ublituximab/oral placebo and teriflunomide/IV placebo). If during an infusion visit, postpone entire infusion visit. If during a non-infusion visit, entire visit can be conducted. MRI can proceed as scheduled.
 
Repeat chemistry testing within 2 weeks. For confirmed liver enzyme(s) Grade 2 or higher, repeat chemistry weekly until <Grade 2.
 
Resume teriflunomide/oral placebo at discretion of PI and/or Treating Neurologist if < Grade 2.
 
Perform the next ublituximab/IV placebo infusion at discretion of PI and/or Treating Neurologist if < Grade 2.

Management of elevated liver enzymes are at the discretion of the PI and/or Treating Neurologist and should be discussed with CRO.	

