¹⁹ Acknowledge completion of 11-day accelerated teriflunomide elimination procedure started at week 100

²⁰ If the subject experiences neutropenia, thrombocytopenia, anemia, or elevated liver enzymes, follow guidelines and procedures on laboratory retests and study treatment per Section 5.2.

²¹ Post Week 24 (including during the Follow-Up Period), urine pregnancy test will be administered every 4 weeks (+/- 5 days). On days when there is not a study visit, the subject will need to perform the test at home and contact the study site to provide the outcome

²² Week 1/Day 1 EDSS must be assessed within 1 day prior to randomization (i.e., on the day before randomization or on the day of randomization but before randomization occurs)

²³ Start 11-day accelerated teriflunomide elimination procedure the day after the early withdraw from treatment visit is completed

²⁴ Pre-medicate 30-60 minutes prior to each infusion of ublituximab/IV placebo with an anti-histamine (diphenhydramine 50 mg or equivalent) and corticosteroid (dexamethasone 10-20 mg or equivalent)

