4. Urine pregnancy test will be performed on a monthly basis, inclusive of the 20 week Follow-up Period. During study visits urine pregnancy tests will be performed at the site and on days of ublituximab or IV placebo infusion urine pregnancy tests will be performed prior to infusion. Post Week 24, urine pregnancy test will be administered every 4 weeks (+/- 5 days), unless serum testing is conducted instead. On days when there is not a study visit, the subject will need to perform at home and provide the outcome to the study staff at the study site. If a urine pregnancy test is positive, the subject should be informed of the potential teratogenic effects, therefore consideration to withhold further teriflunomide/oral placebo dosing should be made and a follow-up appointment should be scheduled as soon as possible where a serum pregnant test will be performed for confirmation.
5. PT/INR should be drawn on Week 1 Day 1 prior to study medications administration. This is the only time PT/INR will be drawn.
6. Quantitative immunoglobulin (IgG, IgM, IgA) test should be analyzed on Week 1 Day 1 (pre-dose) and Week 3 Day 15 (pre-dose), Weeks 24 (pre-dose), 48 (pre-dose), 72 (pre-dose) and 96. Additionally, quantitative immunoglobulin (IgG, IgM, IgA) test will be analyzed for subjects who withdraw from treatment early or have an Unscheduled Relapse Visit.
7. Fibrinogen tests
 - a. All subjects will have 5 serum samples taken prior to the infusions on Week 1 Day 1, Week 3 Day 15 and Weeks 24, 48, and 72. Additionally, fibrinogen will be analyzed for subjects who withdraw from treatment early or have an Unscheduled Relapse Visit.
8. Anti-Drug Antibody (antibodies developed against ublituximab; Central Lab)
 - a. All subjects will have 6 serum samples taken to assess for the presence of ADA prior to the infusions on Week 1 Day 1, Week 3 Day 15 and Weeks 24, 48, and 72. In addition, a serum sample will be taken at Week 96.

[REDACTED]

- a. Serum samples will be drawn from all subjects pre-infusion any time on infusion days of ublituximab or IV placebo and at 30 minutes +/- 15 minutes post infusion on infusion days (Week 1 Day 1, Week 3 Day 15, Weeks 24, 48, and 72). One additional serum sample will be taken on Week 96.

[REDACTED]

[REDACTED]

[figure not shown]
[REDACTED]

[REDACTED]

10. Plasma concentration for teriflunomide

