7.4 BLINDING, PACKAGING AND LABELING

7.4.1 TERIFLUNOMIDE OR ORAL PLACEBO

Each tablet of teriflunomide (14 mg) or oral placebo is a white to off white, round-film-coated tablet with the dose strength "14" engraved on one side and engraved with a "B" on the other side.

Teriflunomide or oral placebo will be supplied to the subject in a box containing 28 tablets (composed of 2 folded blister cards of 14 tablets per blister card as a wallet). Four (4) boxes will be supplied to

the subject every 12 weeks. The packaging of the teriflunomide or oral placebo in the blister pack will be child resistant.

Therefore, to assist in drug accountability for the site, the subjects over 12 weeks should have received 112 tablets and when returning back to the sites in approximately 12 weeks; approximately 84 tablets should have been taken and approximately 28 tablets should be returned to the site. Approximately every 12 weeks, the site must collect all unused teriflunomide or oral placebo tablets.

New boxes of teriflunomide or oral placebo will be provided to the subject. The study site will not re-dispense previously unused tablets back to the subject. These tablets should be quarantined until the study monitor can inventory them and instruct the site on destruction of them.

The box of teriflunomide or oral placebo dispensed to the subject will be labeled in compliance with the applicable regulatory regulations in that country.

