Dispense the next 12-week blister pack of teriflunomide or oral placebo

Timing and Sequence Considerations:

- Prior to infusion
 - Perform urine pregnancy test; *Must have confirmed negative prior to start of infusion*
 - All labs, and ADA, drawn prior to start of pre-treatment and infusion
 - PK
 - Physical examination, EDSS and clinical assessments pre-infusion

- MRI
 - 12 lead ECG
 - Vital signs
- During infusion
- Infusion log
- Post Infusion
- Additional PK 30 minutes +/- 15 minutes after end of infusion
 - 12 lead ECG

Visit:	Week 36 Day 252																								
Time Required:	Approximately 1 hour																								
Treatment:	 Teriflunomide (14 mg) or oral placebo until last day of Week 95																								
Tests:	 Urine Pregnancy Test; Must have confirmed negative result																								
Clinical Assessments:	 Adverse Event  Concomitant medications  Physical examination/vital signs  EDSS, MSFC and neurological examination																								
Labs: (see Laboratory Manual for full details, instructions, and shipping information)	 Hematologic profile; CBC/FBC with differential and platelet count  Serum chemistry panel; 
  
 Serum Chemistry	
   
 Albumin	Glucose	SGPT [ALT]	
 
 Alkaline phosphatase	LDH	Sodium	
 
 Bicarbonate	Magnesium	Total bilirubin	
 
 BUN	Phosphorus	Total Protein	
 
 Calcium	Potassium	Uric acid	
 
 Chloride	SGGT	Indirect/direct bilirubin	
 
 Creatinine	SGOT [AST]		
  
  Pancreatic Enzyme  Absolute B cell lymphocyte count and % B cell  Urinalysis	Serum Chemistry			Albumin	Glucose	SGPT [ALT]	Alkaline phosphatase	LDH	Sodium	Bicarbonate	Magnesium	Total bilirubin	BUN	Phosphorus	Total Protein	Calcium	Potassium	Uric acid	Chloride	SGGT	Indirect/direct bilirubin	Creatinine	SGOT [AST]	
Serum Chemistry																									
Albumin	Glucose	SGPT [ALT]																							

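### Section 3.3.1 requires dosing to be withheld on suspicion of pregnancy but only considered for withholding after a positive urine test, and Section 6.2 item 4 repeats only the softer rule

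*Protocol*

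**What the plan says.** Protocol Section 3.3.1 sets out a sequence. A woman who thinks she may be pregnant must contact the investigator or Treating Neurologist at once. If the investigator suspects pregnancy, "the trial drugs must be withheld immediately, until the result of the pregnancy test is confirmed", and a urine test is done straight away. If that test is positive, she is told of the possible teratogenic effects, and the text continues: "therefore consideration to withhold further teriflunomide/oral placebo dosing should be made and follow-up appointment should be scheduled as soon as possible". The serum test at that appointment is described as the confirmation. If it is positive, all trial drugs stop permanently.

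Section 6.2 item 4 governs routine urine testing: monthly, and every 4 weeks after Week 24. Tests are done at the site during visits. Otherwise, "the subject will need to perform at home and provide the outcome to the study staff at the study site". For a positive result the dosing instruction is "therefore consideration to withhold further teriflunomide/oral placebo dosing should be made and a follow-up appointment should be scheduled as soon as possible". Item 4 contains no mandatory hold, does not mention the infused drug in this context, and does not refer to Section 3.3.1.

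Footnote 21 to Tables 5-7 repeats the home-test duty ("the subject will need to perform the test at home and contact the study site to provide the outcome") and says nothing about dosing.

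Appendix F adds a check at on-site urine tests during treatment. At Weeks 16, 20, 36, 60 and 84, for example, the line reads "Must have confirmed negative result". On Week 3 Day 15 and at Weeks 24, 48 and 72 the negative result must be in hand before the infusion starts.

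**The concern.** The strength of the instruction runs the wrong way. Suspicion alone triggers a compulsory hold of all trial drugs. A positive urine test, which is stronger evidence, triggers only a discretionary decision about one of them. Staff handling a routine test are likely to turn to Section 6.2, where the discretionary sentence is all they find.

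At stake is continued daily intake of a drug for which the protocol itself requires a teratogenicity warning, from the positive urine test to the serum result. The serum appointment is to be made promptly, but no maximum number of days is set.

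**Working it through.** No arithmetic decides this point. The check is a comparison of the texts.

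**1. The steps in order of evidence**

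| Situation | Source | Oral drug | Infused drug |
|---|---|---|---|
| Investigator suspects pregnancy | 3.3.1 | Must be withheld | Must be withheld |
| Urine test positive | 3.3.1 | Consider withholding | Not mentioned |
| Urine test positive | 6.2 item 4 | Consider withholding | Not mentioned |
| Home test done | Footnote 21 | Not mentioned | Not mentioned |
| Urine test before infusion, from Week 3 Day 15 | Appendix F | Not mentioned | No infusion without a negative result |
| Serum test positive | 3.3.1, 7.5.1.1 | Permanent stop | Permanent stop |

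The second and third rows are weaker than the first.

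**2. Can Section 3.3.1 be read consistently?** There are two readings of how long the mandatory hold lasts.

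- It ends with the urine result. A positive result then turns a compulsory hold into an optional one.
- It runs to the serum result, because serum is called the confirmation. The drugs are then already on hold when the urine test turns positive, and there is nothing left to consider.

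The second reading is the sensible one, but it makes the later sentence redundant. On either reading that sentence should change.

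**3. Does the hold reach a routine test?** Its stated trigger is investigator suspicion. A positive scheduled test would ordinarily create suspicion, so the hold arguably applies, but neither section says so.

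**4. Where is the gap?** Infusions from Week 3 Day 15 are protected by Appendix F. At non-infusion visits Appendix F asks for a negative result but states no action on the oral drug. Home tests have no Appendix F line and no staff present. The open interval is therefore daily oral dosing between the urine and serum results, mainly after home tests.

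**5. Does the protocol use firmer wording elsewhere?** Section 5.3 does for graded laboratory abnormalities. For ALT or AST of Grade 2 or higher it instructs: "Withhold study medications (both ublituximab/oral placebo and teriflunomide/IV placebo"). Retesting follows within 2 weeks, and dosing may resume once the value falls below Grade 2. The withhold, retest, resume pattern is thus already in use.

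**6. Would a mandatory hold disturb the primary analysis?** SAP Section 2.1.3.1 measures treatment time from randomization to the last oral or IV dose. A temporary hold followed by resumption leaves both dates, and so the offset, unchanged.

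**The case against.** The best answer is that the rule already exists. Section 3.3.1 is the dedicated pregnancy section, and a protocol is read as a whole. A laboratory schedule that does not restate a safety rule does not cancel it. A woman with a positive home test must contact the site, her report creates suspicion, and suspicion triggers the hold. Section 6.2 also requires counselling and a prompt serum test, and contraception is mandatory. The comparison with Section 5.3 shows only that firm wording is available; the hold on suspicion in Section 3.3.1 is just as firm.

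Most of this stands. It shows that a careful site would probably act correctly. It does not remove the soft sentence from Section 3.3.1, and it relies on the site combining two sections to override the literal wording of the one that schedules the test.

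Three stronger readings are tempting, and the documents do not support them.

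- *The protocol lets a pregnant subject continue treatment.* It does not. Sections 3.3.1 and 7.5.1.1 both require an immediate and permanent stop once pregnancy is confirmed.
- *The fault is simply that Section 6.2 lacks a cross-reference.* A cross-reference would lead to a paragraph containing the same soft sentence, so it would not resolve the conflict.
- *The exposure can be sized from the schedule.* Most 4-weekly tests between Week 28 and Week 92 are at home, and "the subjects over 12 weeks should have received 112 tablets", so a subject would not run out of tablets. Neither fact measures harm. Scheduled tests are not positive results, and tablets in hand are not tablets taken after one.

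**Conclusion.** Section 3.3.1 is internally inconsistent, and Section 6.2 item 4 repeats only its weaker half. Followed literally, the text allows daily oral dosing to continue after a positive urine test until a serum result that has no fixed deadline.

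The practical size is small. The gap concerns only women of childbearing potential with a positive urine test, and mainly tests done at home. It concerns the oral drug and the interval before serum confirmation. With 1:1 randomization, about half of subjects take oral placebo. The expected number of pregnancies, the rate of false positives and the usual delay to the serum test are not given, so no count of affected women or dosing days is offered.

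The conclusion rests on the wording alone. The judgement that the gap is narrow assumes that most sites would treat a positive test as suspicion and apply Section 3.3.1. The point is worth correcting because it concerns subject safety and the correction is cheap; it has no material bearing on the primary analysis.

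**What to change.** In both Section 3.3.1 and Section 6.2 item 4, replace the sentence about considering a hold with:

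> Teriflunomide/oral placebo and ublituximab/IV placebo must be withheld after any positive urine test (site or home) until a negative serum result is available.

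Add to footnote 21 that a subject with a positive home test stops the oral drug and contacts the site the same day.

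The cost is three wording changes, a memo to sites, and a few missed oral doses after false-positive urine tests.

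Two optional tidy-ups could go into the same amendment. The start of washout after confirmed pregnancy could be aligned: it is immediate in Section 7.5.1.1, at the Early Withdrawal visit in Appendix F, and the day after that visit in Section 6.10 and Table 7 footnote 23. The Appendix F checklist for that visit calls for a negative serum pregnancy test, which cannot fit a subject withdrawn because she is pregnant; that condition can be deleted. Neither would justify an amendment alone.
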